Visits 2A&B and 3A&B: Intranasal Oxytocin vs. Placebo Administration. In this double-blinded cross-over placebo-controlled trial of intranasal oxytocin, maternal brain and behavioral responses to infant cues were assessed within and between subjects. Each participant was administered both the active (oxytocin) and inactive (placebo) nasal spray just prior to separate behavioral or fMRI scanning sessions, with the order of administration balanced across subjects. All involved were blinded to the identity of the oxytocin or placebo sprays. Before each visit, the mother was asked to abstain from tobacco, food and drink (except water) for at least 2 hours prior to the visit. We attempted to schedule visits during the latter half of the mother's menstrual cycle, to minimize potential confounding from fluctuations in estrogen levels. Mothers without regular menstrual cycles were attempted to be scheduled one month apart. Mothers who were still breastfeeding were asked to feed their infant at least one hour prior to the visit.

For the four visits involving intranasal drug administration (two behavioral testing visits and two fMRI scanning visits), the following protocol applied: participants were given a urinary pregnancy test prior to the start of each visit. If a mother tested positive, she was excluded from the study due to theoretical concern about possible effects of oxytocin on uterine contraction. Just prior to drug administration, the mother completed the Positive and Negative Affect Scale (PANAS) to rate her current emotions, for comparison to post-spray. The mother then self-administered a dose of either oxytocin (3 puffs per nostril [4 IU per puff] = 24 IU total) or a placebo spray containing only the inactive ingredients of the oxytocin solution. Both experimenters and subjects were blind to the treatment they are receiving. A stopwatch was started at the moment the subjects began the intranasal administration, so that the behavior assessment or fMRI scanning could begin approximately 50 minutes later. Forty minutes after drug administration, the PANAS was repeated.

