14-point sensitivity scale in the CARE-Index. A modified still-face procedure was then conducted. The mother was then taken to another area of the building, while the infant was videotaped to obtain face images used during the subsequent scanning visits. During the brief separation period, the infant was secured in a mounted car seat, and videotaped while using age appropriate toys to elicit smiling (and neutral) facial expressions. This did not usually last no more than 10 minutes. The mother did not observe the videotaping to ensure that each infant face image was novel when presented during the subsequent visits. Crying faces were also elicited by briefly leaving the infant alone in the room, if necessary, secured in the car seat, while the video recorder was running. The infant was observed at all times from behind a one-way mirror, and only left to cry for around 35-40 seconds. Infant cry was also recorded at that time. Infant face images with various degrees of affect—happy, neutral and sad—were then extracted from the digital video recording, for use in the subsequent fMRI procedure (Visit 3). The images were standardized for size, orientation and background using Adobe Photoshop. All of the face images were rated on degree of affect using a 5-point adaptation of the Self-Assessment Manikin (SAM), categorizing each image into one of five affect groups: very happy, happy, neutral, sad or very sad. These faces were matched on age, sex, ethnicity and degree of affect with a large database of “unknown” infant faces, collected during a previous study. Approximately one month later the basic procedure was repeated for each subject, except that those who received intranasal oxytocin were given placebo, and vice versa.

Visit 3A&B: 8-9 Months Postpartum – Brain Response. Around three months after the first behavioral response session, each mother attended two scanning sessions at the Human Neuroimaging Laboratory, Baylor College of Medicine. Intranasal oxytocin or placebo was again administered as described above. Infant face images from Visit 2A were used in the Visit 3A scanning session, and Visit 2B with 3B, to ensure that the repeat scanning session used comparable but unique face images. The images from both sessions were matched on degree of facial affect.

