Next, activation patterns were compared between oxytocin treatment groups and attachment groups using a mixed-model repeated measures analysis of variance (ANOVA), with fixed effects analyses for 1) "infant face category" as a repeated measure within-subjects variable, 2) "oxytocin treatment group" as a within- and between-subjects variable, and 3) "attachment group" as a between-subjects variable. Subjects were treated as a random effect within each group and were used to test for face affect x treatment group x attachment group interaction effects on brain function. Mean beta weights were calculated and compared between the two treatment and attachment groups, in *a priori* regions of interest (VTA, ventral striatum, medial prefrontal cortex), using the t-test and the Mann-Whitney U-test for non-parametric data.

Brain/Behavior Analyses:

The relationship between brain response to the visual infant stimuli described above and interview derived measures was examined within the general linear model framework. Measures examined in this manner included ratings of the stimuli obtained immediately after scanning, adult attachment classifications, and ratings of the parent-infant interaction session ("maternal sensitivity" score). Initially, percent signal change data was extracted from regions of interest, including mesocorticolimbic pathway (VTA, ventral striatum, medial prefrontal cortex), nigrostriatal pathways (substantia nigra, dorsal striatum, dorsolateral PFC), as well as the amygdala, hippocampus, anterior insula and hypothalamus, and was entered into regression models to determine whether there was a linear relationship between brain activation in response to the stimuli and behavioral scores. We focused on these regions given data from animal and human studies reviewed that implicate them in attachment and/or fear neurocircuitry (Leibenluft, Goblin, Harrison et al. 2004a; Lorberbaum, Newman, Horwitz et al. 2002a; Nitschke, Nelson, Rusch et al. 2004; Seifritz, Esposito, Neuhoff et al. 2003; Strathearn et al., 2008; Swanson, 2000). Regression models also tested for group differences in the relationship between brain activation and behavior. Regions of interest were defined using high resolution 3D

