images normalized to standardized stereotactic space (Collins, Zijdenbos, Kollokian et al. 1998). Measures of the striatum included caudate and putamen, outlined on each slice in which these structures were visible. Regression analyses were further employed to identify areas that show a continuous linear dose-response function.

Analyses by Hypotheses:

Since the study is a crossover design, the model initially contains terms testing the order of treatment (oxytocin/placebo) and the interaction between order and treatment to ensure detection of any unexpected carry-over effect from treatment. Since a sufficient washout period was provided and different pictures were shown on the two occasions, we expected these terms to be non-significant, in which case they were removed from the model.

Hypotheses 1-3 was tested using a generalized estimating equation model (SPSS version 17.0), which accounts for repeated measures in the crossover design as well as different types of dependent variables. The basic model contains terms for testing each of these hypotheses including treatment, attachment and treatment x attachment. Interpretation began with the treatment x attachment interaction. If this interaction was not significant, it was omitted from the model. Attachment was initially be treated as a 4-category variable (Types A, B, C and A/C), with the main comparisons being between Types A and B, and between Types C and B. However, we also combined categories to examine secure (Type B) vs. insecure (Types A, C, A/C) attachment. In addition, for the brain-related outcomes, we looked at infant affect as an additional within-subject factor, and examined possible 3-way interactions – treatment x attachment x affect. If this interaction was significant the data was split on attachment group and reanalyzed to assess the treatment x affect interaction within attachment groups. If this interaction was not significant, it was removed. A positive finding for this interaction would indicate splitting on attachment group and reanalysis is in order to assess treatment effect within these groups. Main effects of treatment, attachment, and affect remained in the model. Hypothesis 2(ii) involving counts showed a Poisson distribution outcome while the others showed a normal distribution.

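### The SAP names one pair of tests for the a priori ROI betas; Mann-Whitney or an unpaired t-test on the raw oxytocin and placebo values would ignore the pairing within mothers

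*Combined protocol and SAP*

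**What the plan says.** The SAP section on fMRI Data Processing and Analysis describes a mixed-model repeated-measures ANOVA and then a simpler comparison in three a priori regions (VTA, ventral striatum, medial prefrontal cortex): "Mean beta weights were calculated and compared between the two treatment and attachment groups", "using the t-test and the Mann-Whitney U-test for non-parametric data". One sentence therefore covers two contrasts and names one pair of tests. It does not assign tests to contrasts, does not say whether the t-test is paired or independent, and names no paired rank test.

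The Study Protocol (Visits 2A&B and 3A&B) sets a crossover: "Each participant was administered both the active (oxytocin) and inactive (placebo) nasal spray", "with the order of administration balanced across subjects". Under Visit 3A&B, "each mother attended two scanning sessions at the Human Neuroimaging Laboratory", with a spray given at each.

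Two places mention a between-mother component. The protocol says that "maternal brain and behavioral responses to infant cues were assessed within and between subjects", and the ANOVA enters treatment "as a within- and between-subjects variable". Neither statement is tied to the ROI tests.

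Under Analyses by Hypotheses, Hypotheses 1-3 are tested with a GEE "which accounts for repeated measures in the crossover design". Order and order-by-treatment terms are included at first. The same section says that the count outcome of Hypothesis 2(ii) was Poisson and the other outcomes were normal.

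**The concern.** Attachment differs between mothers, so an independent-samples test suits a two-group attachment contrast with one value per mother. Treatment differs within mothers. The Mann-Whitney U-test assumes independent samples and has no paired form. If the oxytocin betas and the placebo betas are entered as its two samples, each mother appears in both and the test uses the wrong variance. An unpaired t-test has the same fault.

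What is at stake is how to read an ROI p-value for oxytocin versus placebo. From the plan alone, it could come from a paired test, from an unpaired test with the wrong error rate, or from a valid between-mother comparison. These ROIs are the only regions that the plan calls a priori, and the ROI sentence is not labelled as supportive of the GEE.

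**Working it through.** **Inputs from the documents.** Each mother has two scans, one per spray. The tests named are a t-test of unstated type and Mann-Whitney U. The documents give no sample size, alpha, within-mother correlation or spread for the betas, so there is no figure of the plan's own to reproduce.

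**Assumptions.** Number of mothers N = 20, 40 or 60; within-mother correlation rho from -0.2 to 0.7; two-sided 5%; betas normal, heavy-tailed (t with 3 df) or skewed (lognormal, log-SD 0.8).

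**Step 1: approximation.** With N mothers, a common SD sigma and no treatment effect, the variance of the difference in means is 2·sigma²·(1 - rho)/N. An unpaired test uses 2·sigma²/N. Its statistic therefore has SD sqrt(1 - rho) instead of 1, and

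actual size = 2·[1 - Phi(1.96/sqrt(1 - rho))].

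- rho = -0.2: 1.96/1.095 = 1.789, size 7.4%
- rho = 0: 1.96/1 = 1.96, size 5.0%
- rho = 0.3: 1.96/0.837 = 2.343, size 1.9%
- rho = 0.5: 1.96/0.707 = 2.772, size 0.6%
- rho = 0.7: 1.96/0.548 = 3.578, size 0.03%

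**Step 2: simulation of Mann-Whitney on both scans** (20,000 data sets per cell; ranges over the three values of N and the three distributions, which were joined by a Gaussian copula with rho on the underlying normal scale).

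| rho | Actual type I error (nominal 5%) |
|---|---|
| -0.2 | 6.9-7.4% |
| 0 | 4.8-5.1% |
| 0.3 | 2.0-2.2% |
| 0.5 | 0.6-0.9% |
| 0.7 | 0.0-0.2% |

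The simulation agrees with the approximation, and the shape of the distribution matters little for the size.

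**Step 3: the t-test.** On normal data with N = 20 and 40 (4,000 data sets per cell), the unpaired t-test rejected in 1.5-2.1% of null data sets at rho 0.3, 0.7% at 0.5 and 0.1% at 0.7. Over rho 0 to 0.7 the paired t-test and the signed-rank test stayed at 4.0-5.9%.

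**Step 4: power.** For a shift that the signed-rank test detects with 78% power, Mann-Whitney on both scans at rho 0.3, 0.5 and 0.7 had:

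- normal data: 65-67%, 49-51% and 23-25%
- skewed data: 86-87%, 76-78% and 50-60%

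The direction depends on the distribution.

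**Step 5: readings under which the level holds.**

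- The t-test was paired.
- Mann-Whitney was used only for attachment.
- Mann-Whitney compared within-mother period differences between the two order groups. This uses both scans. With an assumed 0.5 SD period effect and balanced order, it kept a type I error of 4.2-5.0%.
- Only first scans were compared. Type I error was 4.1-5.1%, but half the scans go unused.

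**The case against.** The strongest reply is that the pairing is already handled where it counts. The ANOVA in the same paragraph of the SAP treats subjects as random, with treatment at least partly within-subject. The GEE accounts for the crossover and begins with order terms. Mann-Whitney is only a fallback for data unsuited to the t-test, and Analyses by Hypotheses reports every outcome except the counts as normal. If the ROI betas are among those outcomes, the fallback may rarely have been used, and a paired t-test would leave nothing to correct. The sentence may simply list tests for two kinds of contrast, with Mann-Whitney meant for attachment. All the sizes above rest on assumed inputs.

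Most of this stands, and it limits the point to a minor one. It does not remove it. The documents do not list the hypotheses, so placing the ROI betas among the normal outcomes is an inference. The normality statement also leaves open whether the t-test was paired. The ROI sentence names its own tests, for both contrasts, without the order terms used elsewhere.

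A reader might infer more than the documents support:

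- **That a wrong test was used.** The text does not show this; any of the readings in Step 5 is possible.
- **That false positives are inflated.** This needs a negative within-mother correlation, for which the documents give no evidence. With positive correlation the test is conservative.
- **That power is generally lost.** Under skew at rho 0.3 it rises.
- **That Mann-Whitney can never use both scans.** Applied to period differences, it can.

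**Conclusion.** The point holds as a minor one. As written, the plan names a rank test, and a t-test of unstated type, for a contrast that is paired by design. Applied to the raw oxytocin and placebo betas as independent samples, neither an unpaired t-test nor Mann-Whitney holds its nominal level unless the within-mother correlation is zero. For Mann-Whitney the type I error is about 2% at rho 0.3, below about 1% at rho 0.5 or more, and about 7% at rho -0.2. These sizes rest on an assumed N, correlation and alpha; the direction of the error follows from the sign of the correlation alone. The plan states none of the readings that would avoid the problem. The tests of Hypotheses 1-3 are not affected, because the GEE carries them.

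**What to change.** State which test serves which ROI contrast.

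- **Oxytocin versus placebo:** use a within-mother analysis, either a paired t-test or the planned mixed model or GEE with a period/order term.
- **If a rank test is needed:** apply it to within-mother differences. One choice is a rank-sum test of period differences between the two order groups. A signed-rank test will do if no period effect is assumed. The choice matters: with an assumed 0.5 SD period effect (N = 20 and 40, rho 0.3 to 0.7), signed-rank had type I error of 1.0-3.3% and power of 43-73%, against 4.2-5.0% and 74-78% for the period-difference test.
- **Attachment:** keep the independent-samples t-test and Mann-Whitney for two-group contrasts, with one value per mother.
- **If a between-mother treatment comparison was meant:** say so, and say which scans enter it.

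If the tests were already paired, this costs a change of wording. Otherwise it means re-analysing three regions on existing data, with nothing new to collect.

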We will also included in the model stratification variables such as maternal age, ethnicity, breastfeeding status and income. Finally, we explored differences between attachment groups on measures of psychopathology, such as depression (from BDI), anxiety (from SSTA) and parenting experience (from the PSI). If differences emerged between attachment groups in these measures, we considered including them as covariates in analyses.

Hypothesis 4 assessed the correlation between maternal brain reward activation (ventral striatum and medial prefrontal cortex) and three indirect measures of maternal neglect using a linear model.

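### Order and order-by-treatment terms leave the crossover model when non-significant, so period adjustment hangs on a pretest and a weak between-mother test is used to clear carry-over

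*Combined protocol and SAP*

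**What the plan says.** The Study Protocol describes a two-treatment, two-period crossover run twice, at behavioural visits 2A/2B and at scan visits 3A/3B, "with the order of administration balanced across subjects". For the behavioural visits, "Approximately one month later the basic procedure was repeated for each subject".

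Under Analyses by Hypotheses, the SAP says the model at first contains a term for the order of treatment and "the interaction between order and treatment to ensure detection of any unexpected carry-over effect from treatment". Citing a sufficient washout and different pictures at the two visits, it continues: "we expected these terms to be non-significant, in which case they were removed from the model". It gives no significance threshold and no action for a significant result.

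On what is kept, the same section says "Main effects of treatment, attachment, and affect remained in the model". It adds "stratification variables such as maternal age, ethnicity, breastfeeding status and income". If the three-way interaction is significant, "the data was split on attachment group and reanalyzed to assess the treatment x affect interaction within attachment groups". A treatment-by-attachment interaction also leads to a split by attachment group. The separate imaging analysis (fMRI Data Processing and Analysis) is a "mixed-model repeated measures analysis of variance (ANOVA), with fixed effects analyses for" face category, treatment group and attachment group.

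**The concern.** Three things are tied together in one removal rule.

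- **Period adjustment is conditional.** Mothers, infants and familiarity with the procedure can all change between the first and second visit. No listed term absorbs that change once the order terms are removed.
- **The carry-over check is between mothers.** It compares the sum of two visits across sequences, so it carries the full between-mother variation that a crossover is meant to remove. A non-significant result is weak evidence of absence, yet the SAP uses the test to make sure carry-over is detected.
- **The coding of order is not given.** If order means sequence (oxytocin first or placebo first), order by treatment is the period contrast, and the test labelled carry-over would respond to ordinary drift between visits. If order means first or second visit, that mislabelling does not arise.

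At stake is the validity of the crossover treatment estimate. The subgroup estimates are most exposed, because the documents do not say that order was balanced within attachment types.

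**Working it through.** **Inputs.** The documents give the design, the balanced order and the removal rule. They give no sample size, SD, correlation, period effect or alpha for the rule, so there is no stated figure to reproduce. Assumed: two-sided 0.05; within-mother correlation ρ = 0.3 to 0.7; N = 20 to 100 mothers; period effect k = 0.25 to 0.5 SD of the within-mother difference. Steps 2 and 3 are in outcome SDs; steps 4 to 6 are in SDs of the within-mother difference. The two units coincide only at ρ = 0.5.

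**1. What the two terms are.** Code sequence S and period P as ±1 over the four cells: S = (1, 1, −1, −1), P = (1, −1, 1, −1). Treatment is T = S×P = (1, −1, −1, 1). Then S×T = P and P×T = S. So whether order is S or P, the pair {order, order × treatment} is {sequence, period}, and both are subject to removal.

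**2. Carry-over: bias and power.** Let λ be the carry-over of oxytocin minus that of placebo into the second period. Half the difference between sequences in (visit A − visit B) has expectation τ − λ/2, so the bias is half of λ.

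The test of λ compares the mothers' two-visit sums, which have variance 2(1+ρ), between two groups of N/2:

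SE(λ) = √[2(1+ρ)·4/N], with N − 2 degrees of freedom.

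Example: N = 40, ρ = 0.5 gives √(3 × 0.1) = 0.548. For λ = 0.5 the noncentrality is 0.5/0.548 = 0.91.

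| N | Power for λ = 0.5 SD (ρ = 0.7 to 0.3) |
|---|---|
| 20 | 9–10% |
| 40 | 13–16% |
| 60 | 18–22% |
| 100 | 27–34% |

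Power of 80% needs about 330 (ρ = 0.3) to 430 (ρ = 0.7) mothers. The 95% CI half-width for λ is 1.5–1.7 SD at N = 20 and 0.6–0.7 SD at N = 100.

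**3. The same comparison without N.** SE(τ) = √[2(1−ρ)/N], so SE(λ)/SE(τ) = 2√[(1+ρ)/(1−ρ)] = 2.73, 3.46 and 4.76 at ρ = 0.3, 0.5 and 0.7. Suppose the treatment test has 80% power for an effect d, so that d/SE(τ) = 1.96 + 0.84 = 2.80. A carry-over also equal to d has standardised size 2.80/3.46 = 0.81 at ρ = 0.5. Its power is Φ(0.81 − 1.96) + Φ(−0.81 − 1.96) ≈ 0.13. At ρ = 0.3 and 0.7 it is 0.18 and 0.09. Such a carry-over biases the treatment estimate by d/2.

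**4. The pretest on period.** Each mother's oxytocin-minus-placebo difference was simulated as τ + k + e in one sequence and τ − k + e in the other, with e ~ N(0,1) and 400,000 runs per setting. Period was kept if p < 0.05; otherwise it was dropped and the mean difference tested. If period were always dropped, the bias would be k(n₁ − n₂)/N; the pretest removes part of this. Power loss is measured against always keeping period, with τ set for 80% power under balance and, in unequal splits, the bias opposing the effect.

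| Setting | Bias (SD) | Type I error | Power loss |
|---|---|---|---|
| Equal sequences, N = 20–60 | 0 | 4.8–5.0% | under 1 point |
| Assumed 60:40 split, N = 20–60 | 0.002–0.033 | 5.2–5.8% | 0.5–5 points |
| Assumed subgroup of 12, split 8/4 | 0.056–0.082 | 6.0–6.6% | 1–8 points |

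Examples at k = 0.5: a 24/16 split gives bias 0.007, type I error 5.4% and power 76.7% against 78.4%. An 8/4 split gives bias 0.082, type I error 6.6% and power 67.8% against 75.3%.

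**5. How easily a subgroup becomes unbalanced.** With exact balance overall, the number of oxytocin-first mothers in a subgroup of 12 is hypergeometric (12 drawn from N, N/2 per sequence). A split of 8/4 or worse, in either direction, has probability 17%, 30% and 33% at N = 20, 40 and 60.

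**6. Only if order means sequence.** With no carry-over at all, order × treatment tests period, with noncentrality k√N. It is significant with probability 0.19, 0.34 and 0.48 at k = 0.25, and 0.56, 0.87 and 0.97 at k = 0.5 (N = 20, 40, 60).

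These are t-test results for normal outcomes. They approximate the planned GEE tests and do not cover the count outcome in Hypothesis 2(ii).

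**The case against.** The strongest reply is that little harm has been shown. The only documented fact about allocation is that order was balanced, and with equal sequences the pretest on period is practically harmless. The unequal splits are assumptions. The worst case also needs a small attachment subgroup, an appreciable period effect and a significant interaction, since the data are split only then. Even so, the bias of about 0.08 SD compares with a standard error of about 1/√12 = 0.29 SD. All of this stands, and it limits the weight of the period point.

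The carry-over assumption does not rest on the test alone: the SAP also cites washout and different pictures, and the behavioural visits were about a month apart. That is fair. It is also the better ground for the assumption, and it does not make a non-significant test informative.

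Order is partly explained: the SAP attaches the two treatment names to it, which leans towards sequence. The coding is still missing, and under that reading the interaction the SAP assigns to carry-over is the period contrast.

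The list of covariates is open-ended, and the imaging ANOVA treats the treatment factor as both within and between subjects, which might hint at order. Neither passage names a period, visit or order term, so neither can be relied on to supply one.

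Finally, the terms may be removed jointly and not one by one. This changes almost nothing: at 8/4 and k = 0.5, type I error is 6.6% and bias 0.077 SD.

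**Conclusion.** The concern holds. Under either meaning of order, the rule makes both period adjustment and the sequence contrast depend on significance, and no other listed term keeps period in the model.

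The firmer part is the carry-over check. For any plausible correlation it is far weaker than the treatment test: 9–18% power for a carry-over as large as an effect the trial could detect with 80% power. That comparison does not depend on N. Nothing in the documents suggests that a carry-over occurred; the point is that this test could not rule one out.

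The period part is modest. It is negligible if completed sequences are equal and becomes noticeable in small, unequal attachment subgroups, where type I error reaches about 6.6%. All absolute figures rest on the assumed N, ρ, k, alpha and splits. The point should be corrected because the correction is cheap; it is not a fatal flaw.

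**What to change.** - Define sequence (oxytocin first or placebo first) and period (visit A or B) explicitly, for both the behavioural and the scan visits.
- Keep treatment, period and sequence in every crossover model whatever their p-values, including models split by attachment group. State whether the same terms enter the imaging ANOVA.
- Delete the removal rule, and refit any models from which the terms were already dropped.
- Rest the no-carry-over assumption on the single administration per visit and the actual intervals between visits. State the interval between 3A and 3B. At present about one month is given for 2A/2B, and otherwise one month appears only as a scheduling aim for mothers without regular cycles.
- Report the sequence contrast with its 95% confidence interval as description, not as a pass/fail check.

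The cost is SAP wording, one or two degrees of freedom per model and the refitting. Treatment order and visit are known by design, so no new data are needed.

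### In the brain-outcome GEE, treatment x affect is specified only within attachment groups after a significant three-way interaction, so the plan names no test for an affect-dependent oxytocin effect shared by all mothers

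*Combined protocol and SAP*

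**What the plan says.** The GEE for Hypotheses 1-3 is described in the SAP under Analyses by Hypotheses. Its starting point is: "The basic model contains terms for testing each of these hypotheses including treatment, attachment and treatment x attachment". For the brain outcomes the plan adds "we looked at infant affect as an additional within-subject factor" and says that it "examined possible 3-way interactions" of treatment, attachment and affect.

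The next step depends on that result. With a significant interaction: "If this interaction was significant the data was split on attachment group and reanalyzed to assess the treatment x affect interaction within attachment groups". Otherwise: "If this interaction was not significant, it was removed". A further sentence says that a positive finding for this interaction leads to a split on attachment group to look at the treatment effect. The paragraph then states: "Main effects of treatment, attachment, and affect remained in the model".

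A second brain analysis appears under fMRI Data Processing and Analysis. It is a mixed-model repeated measures ANOVA with treatment, attachment and infant face category as factors, the last entered "as a repeated measure within-subjects variable". The only interaction named there is the three-way one. The earlier two-factor ANOVA in that section crosses infant identity with affect and has no treatment factor.

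**The concern.** The three-way interaction and the pooled treatment x affect interaction answer different questions. The first asks whether attachment types differ in how oxytocin's effect depends on the infant's expression. The second asks whether it depends on expression at all. The plan uses the first as the condition for looking at the second, and then looks only inside attachment groups.

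Happy and sad faces are separate predictors in the fMRI design matrix, and the stated purpose is to explore how oxytocin modifies maternal responses to infant cues. If the drug raises the response to one expression and leaves the other alone or lowers it, in all attachment types alike, the rule drops the affect structure in just that case. What is left is a treatment effect averaged over expressions, which understates the effect on the responsive expression and may be reported as no effect.

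**Working it through.** **1. What each test asks.** In attachment type g, let H(g) and S(g) be the oxytocin-minus-placebo effects on happy and sad faces, and let D(g) = H(g) - S(g).

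- Three-way null: D(A) = D(B) = D(C) = D(A/C).
- Pooled treatment x affect null: the average of D(g) is 0.
- Treatment main effect: the average of (H + S)/2.

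If D(g) equals the same non-zero value in every type, the three-way null is true and the pooled null is false. This follows from the stated rule and needs no numerical assumption.

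**2. Inputs.** The plan has no figure to reproduce: it gives no sample size, alpha, effect size or SD. The following are assumptions: two-sided alpha 0.05; 20 to 60 mothers; two affect levels, as in the SAP's design matrix; SD 1 for the within-mother oxytocin-placebo difference on each face type; correlation r = 0.2 or 0.5 between the happy and sad differences; effect d = 0.6 on happy faces and k x 0.6 on sad faces, the same in every attachment type.

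**3. How often the follow-up is reached.** The three-way test was simulated as a one-way ANOVA of the happy-minus-sad difference over four or two attachment groups, with effects +0.6 and -0.6, r = 0.5 and N = 20, 40, 60 (10,000 runs each). It was significant in 0.048 to 0.053 of runs. A robust (sandwich) Wald test on 3 df, closer to what a GEE would use, rejects in about 14%, 12% and 9% to 10% at 8, 10 and 15 mothers per type. That is small-sample inflation of the false-positive rate, not sensitivity to the shared effect.

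**4. What the main effect and a pooled contrast would detect.** Power = Φ(t - 1.96) + Φ(-t - 1.96), with

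- main effect: t = |(1 + k)d/2| x √N / √((1 + r)/2)
- pooled treatment x affect: t = |(1 - k)d| x √N / √(2(1 - r))

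Example with N = 30, k = 0, r = 0.5. Main effect: 0.30 x 5.477 / 0.866 = 1.897, power 0.475. Pooled contrast: 0.60 x 5.477 / 1 = 3.286, power 0.908.

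Results at N = 30 (range over r = 0.2 and 0.5):

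| Sad effect as multiple of happy (k) | Average effect (SD) | Main-effect power | Pooled treatment x affect power |
|---|---|---|---|
| -1 | 0.00 | 0.05 | 0.999 or more |
| -0.5 | 0.15 | 0.158-0.186 | 0.974-0.999 |
| 0 | 0.30 | 0.475-0.564 | 0.738-0.908 |
| 0.5 | 0.45 | 0.812-0.889 | 0.255-0.376 |

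Over N = 20 to 60, main-effect power is 0.34 to 0.85 at k = 0 and 0.64 to 0.99 at k = 0.5.

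**5. Sensitivity to the assumed effect.** With a double difference of 0.5 of its own SD, a direct test has about 79% to 97% power at 32 to 60 mothers. With 0.2 SD it has about 20% to 33%. The gain from adding the test depends heavily on an input that the documents do not supply.

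**The case against.** **The ANOVA may already cover it.** A reader might infer that a shared treatment x affect effect is never tested. The documents do not support that. The mixed-model ANOVA has face category and treatment as factors, and a standard factorial fit would produce their two-way term over all mothers. Naming the three-way interaction does not exclude lower-order terms. This stands: the accurate statement is that no pooled test is specified. It does not close the point, because the GEE is the stated test of Hypotheses 1-3, and a by-product of another model is not a planned test.

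**The effect need not average out.** Full cancellation requires equal and opposite effects. In other cases the main effect is diluted, and when both expressions move the same way (k = 0.5 above) it is the stronger of the two tests. This also stands.

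**The listed terms might be fitted literally.** A reader might infer that the three-way term is entered without treatment x affect and attachment x affect. With 2 x 4 x 2 = 16 cells and 1 + 1 + 3 + 3 + 1 = 9 lower-order parameters, it would then carry 16 - 9 = 7 df instead of 3 and could label a shared effect as attachment-specific. The text does not establish this. The basic term list is introduced with the word 'including' and so is not closed. That reading also conflicts with the claim that the effect goes untested, since the within-group follow-up would then be reached often.

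**The text is ambiguous.** Consecutive sentences refer to 'this interaction' without saying which one. The second, about the treatment effect within groups, fits treatment x attachment and may imply a step-down. Even so, no step names treatment x affect for all mothers.

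**It may not be a hypothesis.** The wording of Hypotheses 1-3 is not in the documents, affect is introduced as an addition to the basic model, and the purpose is exploratory. This limits the weight of the point.

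**Conclusion.** The point holds for the GEE as written. Treatment x affect is reached only through a test of a different null, so a pattern common to all attachment types gets through at about the false-positive rate: 5% for an exact test, and roughly 9% to 14% for a small-sample robust Wald test at 8 to 15 mothers per type. When it does get through, it is examined within attachment groups, not pooled. The main effect left in the model is diluted, or cancelled in the equal-and-opposite case.

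The logic needs no assumed numbers, but every power figure does and is illustrative only. The documents do not show that the effect went untested, that it would average to zero in general, or that the three-way term was fitted on 7 df. This is a worthwhile and inexpensive improvement in specification, not a defect that invalidates the plan.

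**What to change.** In Analyses by Hypotheses:

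- Fit the brain-outcome GEE with treatment x affect, attachment x affect and treatment x attachment all beneath the three-way term.
- Estimate and report treatment x affect across all mothers whatever the three-way result, with oxytocin-minus-placebo effects shown separately for happy and sad faces.
- Keep treatment x affect in the model if the three-way term is dropped.
- Say which interaction each 'this interaction' sentence means, and which two-way terms stay at each step.

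In fMRI Data Processing and Analysis, state whether the mixed-model ANOVA reports face category x treatment, and align it with the GEE. Much of the text is in the past tense; if the analyses have been run, label the added test as such.

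The cost is SAP wording and no new data. With four attachment types and two affect levels, treatment x affect adds 1 parameter and attachment x affect adds 3, so at most 4 in all. There is one more reported test per brain outcome, which should be counted in the multiplicity correction.
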